11.3.2. Study Population and Sample Size

The study population for this clinical trial includes 12,000 males and non-pregnant females, ≥ 50 years old, inclusive, who meet all eligibility criteria. The participants will be recruited from the general population. At least half of the participants will be ≥ 65 years old.

The study sample size of 12,000 subjects is based on the lower bound of the two-sided 95% confidence interval for vaccine efficacy (VE) being above 40% with 80% probability when true VE is 62%. It assumes 1:1 randomization, a 2.41% attack rate in the study population, and no more than 10% of subjects lost to follow-up or excluded from the per protocol population. Under these assumptions, 182 first episodes of qRT-PCR -confirmed influenza of any strain occurring at least 15 days after the second dose of study vaccine or control and prior to the end of the first influenza season will be needed to demonstrate efficacy is at least 40%.

A total of up to 10 sites will be selected to participate to the CMI substudy. A total of 350 subjects will be randomly chosen among 700 subjects from the selected sites: approximately 263 subjects selected at random from 350 M-001 subjects and approximately 87 from 350 placebo subjects; placebo subjects being selected to maintain the study blind. Assuming that among the 263 M-001 selected subjects, 210 will have valid measurement for the change from baseline in percentage of CD4⁺ lymphocytes producing Th1 cytokine (e.g. INF- γ) in response to any of the 9 peptides in M-001, then this endpoint can be estimated with a precision of at most 2% (1/2 width of the 95% CI).

11.3.3. Subject Enrollment and Follow-up

Based on the accrual rate for similar studies, it seems reasonable to expect that the participating sites will be able to enroll this trial in a timely fashion. Prior experience suggests up to 10% of subjects may be excluded from the per protocol analysis for the primary outcome either because they were lost-to-follow-up or otherwise do not have data available following the study vaccination or because they had a protocol deviation requiring their exclusion from the per protocol analysis.

11.4. Planned Interim Analyses

Interim unblinded analyses would be used to terminate this trial in the event that unanticipated safety events deemed to be of sufficient concern require such action by the sponsor. Sample size re-estimation at the end of Year 1 and possibly at the end of Year 2 will be based on the pooled number of influenza cases in the PP population and not on any interim estimate of efficacy or the observed attack rate in the control group. Details of the sample size re-estimation will be provided in the DSMB charter.

11.4.1. Interim Safety Review

A DSMB will be convened by the sponsor to review study progress and participant, clinical, safety, reactogenicity, and efficacy data as described in section 9.5. Once the last subject in Year 1 completes the visit that occurs approximately at Day 202, the clinical database will be cleaned, monitored and analyzed in blinded manner. The first partly unblinded report will be issued to the DSMB at the end of the first influenza season of the trial approximately in June 2019, though some

data may be requested by DSMB to be provided to them earlier. Based on the interim review of safety data, the DSMB may recommend continuing the study as planned, stopping the study for safety concerns, or modifying the study to ensure study objectives are followed.

11.4.2. Interim Efficacy Review

There are no plans to stop the trial for futility or for efficacy at the end of Year 1. However if after the first flu season the total number of per protocol cases of confirmed influenza infection is substantially fewer than there may be a decision made by the Sponsor about increasing the sample size for Year 2.

11.5. Final Analysis Plan

At the end of Year 2 a clinical study report (CSR) will be prepared (unless the study is decided to be continued for Year 3) summarizing the efficacy, safety, reactogenicity, and immunogenicity data. The clinical database will be cleaned, monitored, and locked prior to analysis.

A formal statistical analysis plan for the efficacy and immunogenicity data will be developed and finalized prior to start of the study. Any changes to the plan including post hoc analyses will be documented and clearly indicated in the CSR.

11.5.1. Analysis Populations

The Safety Analysis population includes all subjects who received at least one dose of study vaccine. Subjects in the safety population will be analyzed according to the treatment actually received.

The intent-to-treat (ITT) population includes all subjects who received at least one dose of study vaccine. Subjects in the ITT population will be analyzed according to their randomization.

The per protocol (PP) population includes all subjects in the ITT subset satisfying the following criteria:

- Subject met all protocol-specified inclusion criteria and met no exclusion criterion,
- Subject received both doses of M-001/placebo as randomized, in the protocol-specified time frame, and at the intended dose level,
- Subject did not receive M-001/placebo that was not properly handled or was otherwise not acceptable for administration,
- Subject had at least one successful surveillance contact 15 days or more after the second dose of M-001/placebo, or attended at least one ILI visit due to ILI symptoms
- Subject did not receive a seasonal influenza vaccine between randomization and end of the surveillance period for Season 1,
- Subject did not receive a licensed live vaccine within 30 days of any dose of M-001/placebo, and
- Subject did not receive a licensed non-live vaccine within 21 days of any dose of M-001/placebo.

11.5.2. Analysis of Safety Data

Summaries and analysis of safety data will be presented for the Safety Analysis Population.

Solicited events will be summarized by severity for each day after each study vaccination (Days 0-7 post each study vaccination, 8 days in total) and as the maximum severity over all 8 days (day of the vaccination inclusive). Additionally, solicited events will be analyzed by taking the most severe response over the follow-up period and using standard techniques, such as exact confidence intervals, to summarize the proportion of subjects reporting each symptom, any injection site symptom, and any systemic symptom. Summaries of solicited events will be presented separately for each study vaccination as well as overall study vaccinations by treatment arm. The proportion of subjects reporting symptoms may be compared between treatment arms using Chi-square or Fisher's exact test, as appropriate. The proportion of subjects reporting solicited symptoms between the different study vaccinations (e.g., dose 1 vs. dose 2) will be compared using McNemar's test.

Unsolicited AEs will be coded by Medical Dictionary for Regulatory Activities (MedDRA[®]) for preferred term and system organ class (SOC). The number of SAEs is expected to be small in this trial and SAEs will be reported by detailed listings showing the event description, MedDRA[®] preferred term and SOC, relevant dates (study vaccinations and AEs), severity, relatedness, and outcome for each event. Non-serious unsolicited AEs will be summarized as number and percentage of subjects reporting at least one event in each MedDRA[®] preferred term and SOC, cross tabulated by severity and relationship to study product. Additionally, the proportion of subjects and exact 95% confidence intervals of AEs in aggregate and by MedDRA[®] categories will be computed.

Graphical presentations may include box plots and shift plots.

11.5.3. Analysis of Efficacy Data

Primary Efficacy Assessment

For the primary analysis of vaccine efficacy (VE), the efficacy of M-001 after a first influenza season in each cohort will be estimated by

$$VE = 1 - [(C_V / N_V) / (C_P / N_P)]$$

where C_V and C_P are the number of per protocol cases of influenza meeting the primary case definition in the vaccine and placebo group, respectively, and N_V and N_P are the number of per protocol subjects in the vaccine and placebo group, respectively. The confidence interval for VE will be calculated by the Clopper-Pearson exact method conditional on the total number of cases in the vaccine and placebo groups combined. Similarly, vaccine efficacy and its 95% confidence interval will be calculated for the ITT population.

VE and its 95% confidence interval will be estimated by age group (i.e., < 65 years, ≥ 65 years) for both the PP and ITT analysis populations. Given VE for a specific age group can be approximated

by 1 minus the age group specific odds ratio, the Breslow-Day test for the homogeneity of the odds ratios will be used to test for a common VE across age groups. In addition, given that circulating strains of flu may vary over the course of the trial, VE and its 95% confidence interval will be estimated by flu season as well for both the PP and ITT analysis populations; Breslow-Day test for the homogeneity of the odds ratios will be used to test for a common VE across cohort (flu season).

If the study discontinuation or loss to follow-up rate varies by vaccine group, a Cox proportional hazards model will be used to estimate vaccine efficacy. For this analysis, time from 15 days after the second dose of study vaccine or placebo to the first episode of culture or PCR confirmed influenza caused by any influenza A or B virus in association with a protocol-defined influenza like illness (ILI) will be the endpoint. All subjects will be censored at the earliest of their date of study withdrawal, date of lost to follow-up, or end of their first influenza season defined as April 30th for countries in the northern hemisphere. The model will have a single covariate for vaccine group and will be stratified by age group. Vaccine efficacy will be estimated by 1 minus the estimated hazard ratio from this model. If the lower limit of the 95% confidence interval for vaccine efficacy based on the PP population is above 40%, the vaccine will have demonstrated sufficient efficacy.

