5.3. Treatment Assignment Procedures

5.3.1. Randomization Procedures

Central randomization will be implemented in this study. Subjects will be randomized to 1 of 2 treatment arms, based on a computer-generated randomization schedule prepared by or under the supervision of the sponsor before the study. The randomization will be stratified by cohort and age group (i.e., 50- 65, ≥ 65) and balanced by using permuted blocks. At least 50% of study participants will be 65 or older in each randomization cohort. The Interactive Web Response System (IWRS) will assign a unique treatment code, which will dictate the treatment assignment and matching study drug kit(s) for the subject.

For season 2, the randomization will be further stratified by sub-study participation (i.e. Yes or No).

For the CMI substudy, 350 subjects from sites participating to the sub-study (sub-study sites) are randomly chosen among 700 sub-study sites subjects with approximately 263 subjects selected at random from 350 M-001 sub-study sites subjects and approximately 87 from 350 placebo sub-study sites subjects.

Once consented and upon entry of demographic data and confirmation of eligibility for this trial, the subject will be enrolled. A total of 12,000 subjects will be randomly assigned to one of 2 arms: experimental and control. A total of 700 subjects will be randomly chosen to participate to the sub-study, with approximately 263 subjects selected at random from 350 M-001 sub-study sites subjects and approximately 87 from 350 placebo sub-study sites subjects.

The investigator will not be provided with randomization codes. The codes will be maintained within the IWRS, which has the functionality to allow the investigator to break the blind for an individual subject, if necessary.

Per International Conference on Harmonisation (ICH) guideline E6: Good Clinical Practice (GCP), screening records will be kept at each participating site to document the reason why an individual was screened, but failed trial entry criteria.

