11.3. Sample Size Considerations

11.3.1. Study Design

This is a pivotal, multicentre, randomized, modified double-blind, placebo-controlled phase 3 trial to assess the safety and clinical efficacy of M-001, an influenza vaccine administered intramuscularly twice in older adults and the elderly (≥ 50 years of age). Subjects will be randomized 1:1 to vaccine or placebo with randomization stratified by cohort and age group. For season 2, stratification will also be performed for participation to the sub-study. All doses will be administered IM approximately 21 days apart (recommended window is 21-30 days). All subjects from cohort 1 will be followed for up to two consecutive influenza seasons with no obligation to continue in season 3 if the study is extended to third season with protocol amendment. It is not planned to extend the participation of the cohort 1 subjects beyond season 1. Subjects from cohort 2 will be followed up for one season. If the study is extended to third season with protocol amendment, it will be determined by the amendment if they are offered possibility to continue their participation in the next season and new, relevant consent will be then collected.

A total of up to 10 sites will be selected to participate to the CMI substudy. Blood samples will be collected prior to the first study vaccination (Day 0) and approximately 15 days (day of the vaccination inclusive) after the second vaccination (Day 36, 14 ± 2 days since day of the second vaccination) in 350 randomly chosen subset of subjects from these sites. M-001 subjects will be 3 times more likely to be selected in the subset than placebo subjects and T cell responses will be measured only in subjects who receive M-001.

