Descriptive statistics of  $p_V = C_V / N_V$  and  $p_P = C_P / N_P$  by country and site within country will be provided,  $N_V$  et  $N_P$  being the number of subjects and  $C_V$  and  $C_P$  being the number of cases, within each country, and site within country.

Sensitivity analyses for the primary efficacy endpoint:

Time to first qRT-PCR- or culture-confirmed influenza in association with a protocol-defined ILI will be considered.

For this analysis, performed on the PP set, the following proportional hazard model will be fitted:

$$h(t) = h_0(t) \exp[\beta_1 \text{ Group}]$$

where  $h_0(t)$  is the baseline hazard function, Group is the treatment variable, (0 for placebo and 1 for M-001), and  $\beta_1$  is the group effect.

The proportional hazard model assumes that the ratio of the hazard functions associated with M-001 and placebo is constant over time.

Under this model, the VE between M-001 and placebo is estimated by  $100(1 - e^{\beta_1})$  and its associated 95% CI will be derived as  $100(1 - e^{\beta_1 \pm z_{0.975} \text{sterr}(\beta_1)})$ , where  $\text{sterr}$  and  $z_{0.975}$  represents the standard error and 97.5% quantile for the normal distribution, respectively.

The p-value resulting from the test of  $H_0: \beta \geq \ln(0.6)$  versus  $H_a: \beta < \ln(0.6)$  will be reported (test will be performed at the one-sided level 0.025).

In addition, the time to first qRT-PCR- or culture-confirmed influenza in association with a protocol-defined ILI will be presented using a Kaplan-Meier plot, with x-axis values at 30, 60, 90, 120, 150, 180, 210 and 240 days.

For the time-to-event analysis, the time of the first qRT-PCR or culture confirmed influenza in association with a protocol-defined ILI is the time of the first symptom associated with the ILI episode. This time will be calculated in days from the start of the surveillance period (14 days post second vaccination). Subjects without qRT-PCR- or culture-confirmed influenza will be censored at the last successful contact and the associated time in the analysis will be the number of days from the start of the surveillance period (14 days post second vaccination) until censoring time. For the ITT analysis, subjects with no surveillance contact will be censored at day 1.

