Additional analyses will be performed to assess the effect of the 2 cohorts (season 2018-2019 and season 2019-2020) and the age stratification factor (<65 years and  $\geq 65$  years) in the model applied to time to first qRT-PCR- or culture-confirmed influenza in association with a protocol-defined ILI. The methodology will be based on the paper by Mehrotra, Lu, and Lixix. The hazard ratio will first be estimated separately for each of the 4 strata (combinations of cohort and age group) using an unstratified Cox model and the stratum-specific estimates will be combined using the minimum risk weights.

*qRT-PCR Cut-off for confirmation of influenza in association with a protocol-defined ILI*

An additional sensitivity analysis to the primary efficacy assessment will be performed where qRT-PCR- confirmed influenza is defined if the qRT-PCR Ct count corresponding to the detection of any flu type is  $< 40$ .

The analysis will be the same than the one described for the primary efficacy endpoint.

Secondary efficacy endpoints:

The first secondary efficacy assessment will be analyzed using the same methodology as the one used for the primary outcome(including the supportive and sensitivity analyses). Notice that samples with cycle threshold (Ct)  $\leq 35$  only were grown for culture.

The second secondary efficacy assessment consisting in the between-group difference in number of days with respiratory or systemic symptoms will be assessed within the subjects with qRT-PCR- or culture-confirmed influenza illness from the per-protocol population. The number of days with respiratory or systemic symptoms during the first qRT-PCR- or culture-confirmed ILI event will be used in the analysis.

The between-group comparison will be done on the percentage of subjects with number of days with respiratory or systemic symptoms in the following categories:

- $< 7$  days
- $\geq 7$  and  $< 14$  days
- $\geq 14$  and  $< 21$  days
- $> 21$  days

using Cochran-Mantel-Haenszel test (general association statistic) with 4 strata corresponding to the combination of age category and cohort.

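### The protocol's fallback Cox model leaves out cohort, a randomisation stratum, and the SAP keeps its cohort-by-age Cox analysis as an additional one; under specific loss patterns this biases VE slightly

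*Protocol*

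**What the plan says.** **Randomisation.** Protocol 5.3.1: "The randomization will be stratified by cohort and age group". Section 11.3.1 repeats it: "Subjects will be randomized 1:1 to vaccine or placebo with randomization stratified by cohort and age group". Season 2 adds sub-study participation as a stratum. The two cohorts are the 2018-2019 and 2019-2020 seasons.

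**Protocol Cox model (11.5.3).** "If the study discontinuation or loss to follow-up rate varies by vaccine group, a Cox proportional hazards model will be used to estimate vaccine efficacy". No threshold or test defines when the rate varies. On its terms: "The model will have a single covariate for vaccine group and will be stratified by age group". The paragraph ends with the success rule: "If the lower limit of the 95% confidence interval for vaccine efficacy based on the PP population is above 40" per cent, efficacy is sufficient.

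**SAP Cox models (5.2 and 5.4.2).** The Cox model is a sensitivity analysis. Its first form contains treatment only: "Group is the treatment variable, (0 for placebo and 1 for M-001"). The one-sided 0.025 test against ln(0.6) is stated for this model. Next comes: "Additional analyses will be performed to assess the effect of the 2 cohorts" and of age. Here hazard ratios are estimated in each of the four cohort-by-age strata and combined with minimum risk weights. The table list labels a cohort-and-age Cox table for PP (14.2.21.2); the ITT Cox table (14.2.21.3) has no such label.

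**SAP decision rule (5.4.1 and 5.4.2).** Success is judged on the exact conditional interval in the PP set, both cohorts combined.

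**SAP section 11.** Its list of changes from protocol version 5.0 mentions neither the different strata nor the changed role of the Cox model.

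**The concern.** The two cohorts were followed in different influenza seasons, and the protocol plans VE by season "given that circulating strains of flu may vary over the course of the trial". With one baseline hazard for both seasons, each risk set mixes people from a higher-risk and a lower-risk season. At randomisation the mix is the same in both arms. If the arms then lose people unequally, and more so in one season than the other, the mixes diverge and the hazard ratio picks up a season effect.

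The protocol calls on this model only when loss differs by arm, which is when the mixes could diverge. The resulting VE is compared with a fixed 40% bar, so an upward shift inflates type I error and a downward shift costs power.

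The omission is also out of line with the rest of the plan. Protocol 11.5.3 puts season/cohort in the secondary ANOVA and Poisson models. The SAP uses four cohort-by-age strata for symptom duration and ILI percentage, and has cohort in its Poisson model.

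**Working it through.** **1. The plan's own figure.** With 1:1 allocation, the M-001 share of cases is 0.60/1.60 = 0.375 at VE 40% and 0.38/1.38 = 0.2754 at VE 62%. With 182 cases the exact interval succeeds at 55 or fewer M-001 cases. Power is 0.815 and one-sided error 0.0242, which agrees with the stated 80%. Expected cases are 12,000 × 0.9 × 0.0241 × 1.38/2 = 179.6, close to 182, if 2.41% is read as the placebo rate. That reading is used below.

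**2. Approximate formula.** For rare events and loss before the season, a Cox model without cohort strata estimates about HR × R. R is the average placebo-level attack rate over the M-001 risk set divided by the same average over the placebo risk set.

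From the documents: per arm, about 2,027.5 in cohort 1 (2,027 and 2,028) and 4,000 in cohort 2. Assumed, because the documents give no such figures: attack rates by season, loss by arm and season, timing of loss and shape of the season.

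**3. Worked example.** Placebo attack rates 1.2% and 3.02% (weighted mean about 2.41%). Cohort 1 loses 10% in each arm (1,824.75 remain). Cohort 2 loses 5% on placebo (3,800 remain) and 15% on M-001 (3,400 remain).

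- M-001: (1,824.75 × 1.2 + 3,400 × 3.02)/5,224.75 = 2.384
- Placebo: (1,824.75 × 1.2 + 3,800 × 3.02)/5,624.75 = 2.430
- R = 0.9814 (from unrounded values)
- True VE 62%: 1 − 0.38 × 0.9814 = 62.7%
- True VE 40%: 1 − 0.60 × 0.9814 = 41.1%

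At VE 40% the cases are about 74.7 and 136.7, so SE = √(1/74.7 + 1/136.7) = 0.144. With ln R = −0.0188, one-sided error is Φ(−1.96 + 0.0188/0.144) = 0.034.

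**4. When R = 1.** If both seasons have the same attack rate, both averages equal it. If the arm difference in loss is the same in both seasons, the retention factors cancel within each arm.

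**5. Full calculation.** The expected Cox score equation was solved numerically, which also allows for depletion of the risk sets and for loss spread uniformly over the season. Cohort 2 loses 5% on placebo and 15% on M-001; cohort 1 loses 10% in both arms.

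| Placebo attack rate, season 1 / 2 | Timing of loss | Shift at VE 62% (points) | Shift at VE 40% (points) | One-sided error at VE 40% |
|---|---|---|---|---|
| 1.2% / 3.0% | early | +0.7 | +1.1 | 0.034 |
| 1.2% / 3.0% | uniform | +0.3 | +0.5 | 0.029 |
| 0.6% / 3.3% | early | +1.0 | +1.6 | 0.038 |
| 0.6% / 3.3% | uniform | +0.4 | +0.7 | 0.030 |
| 4.8% / 1.2% | early | −1.6 | −2.5 | 0.0125 |
| 4.8% / 1.2% | uniform | −0.8 | −1.2 | 0.018 |

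The largest error for a 10-point difference in one season is 0.043: rates 4.8%/1.2%, the difference in cohort 1 only, early loss, VE 42.1% at true 40%.

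Controls: with equal attack rates the shift is 0.00 under every loss pattern. With 5% v 15% loss in both seasons it is −0.04 to −0.15 points, the same as with 10% loss everywhere. Stratifying by cohort returned the true VE and 0.025 in every scenario. Age strata were not modelled, as they do not affect the cohort question.

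**The case against.** Three stronger readings are tempting, and the documents do not support them.

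- *The SAP never adjusts the Cox model for cohort.* It does. SAP 5.4.2 plans the four-stratum combination and lists a table for it. What remains is its rank: it is additional, has no stated test against ln(0.6), and is labelled in the table list for PP only.
- *The trial's success hangs on this model.* Under the SAP it does not; the exact PP analysis decides. Protocol 11.1 also says the hypothesis is tested with the Clopper-Pearson interval. Only the Cox paragraph in protocol 11.5.3, read with the rule that closes it, lets the Cox model decide. That tension needs resolving, but restratifying would not alter the SAP's decision.
- *Any dropout that differs by arm biases VE.* It does not. Both conditions in the working must hold, and no document predicts them. The protocol says that strains may vary and allows for a mild season; it does not forecast unequal attack rates.

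The size can fairly be challenged too. The plan allows up to 10% lost or excluded and expects minimal missing data. In the worked example the log hazard ratio moves by 0.0188 against an SE of 0.144, about one-eighth of a standard error. Opposite 20-point differences in the two seasons can move VE by 4 to 10 points, but those inputs are extreme. VE by cohort, the Breslow-Day test by cohort and Kaplan-Meier curves by season would help to expose a season imbalance.

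All this limits the importance of the point. It does not justify omitting a randomisation stratum from the one model reserved for unequal loss.

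**Conclusion.** The point holds as a modest analysis and consistency defect. Three facts are plain in the text: cohort is missing from the protocol's fallback Cox model, the SAP's first Cox model has no strata, and SAP section 11 declares neither that change nor the model's new role.

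For an assumed 10-point arm difference in loss confined to one season, with unequal attack rates, the shift is about 0.3 to 1.6 points at true VE 62% and about 0.5 to 2.5 points at true VE 40%, in either direction. Where it is upward, one-sided error is about 0.029 to 0.043; where it is downward, error falls below 0.025. With equal attack rates, or the same arm difference in both seasons, the bias is 0 to 0.15 points.

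These sizes rest on assumed seasonal rates, loss and timing; the mechanism and the text discrepancy do not. The change is worth making because cohort stratification removed the bias in every scenario and costs almost nothing.

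**What to change.** 1. Protocol 11.5.3: state that the Cox model is stratified by cohort and age group.
2. SAP 5.4.2: make one cohort-by-age Cox analysis the main one, for both PP and ITT, and attach the test against ln(0.6) to it. Say which is meant: a Cox model with four strata, or the already planned combination of stratum-specific estimates with minimum risk weights. They are different methods; the SAP's cited source presents the second as an alternative to the stratified model. Keep the model without strata as supportive if wanted, and add the matching ITT table.
3. Reconcile the Cox model's role. Either it is a sensitivity analysis in both documents, or it replaces the exact analysis under a stated trigger that says what counts as loss varying by arm. Record the outcome, and the change of strata, in SAP section 11.

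The cost is a phrase in the protocol, a short edit to the SAP and its table list, and a small programming change. Cohort and age group are already recorded for everyone, so no new data or participants are needed. It should be settled before unblinding.
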